9.5 SECONDARY EFFICACY ENDPOINTS

The secondary efficacy endpoints are as follows:

- Change from baseline in the weekly average of daily WPI scores at Week 12 of the Double-Blind Treatment Phase, based on an NRS-11;
- Percentage of subjects with a 30% and 50% or greater decrease in API from the Open-Label Titration Phase baseline to Week 12 of the Double-Blind Treatment Phase;
- Time to loss of efficacy, defined as discontinuations from the study or study drug for lack of efficacy;
- Change from baseline to Week 12 of the Double-Blind Treatment Phase in the PGI-I scale (as assessed by each subject)
- Change from baseline to Week 12 of the Double-Blind Treatment Phase in WPAI scores;
- Change from baseline to Week 12 of the Double-Blind Treatment Phase in EuroQoL Group EQ-5D-5L scores; and
- Rescue medication days during the Double-Blind Treatment Phase.

9.5.1 CHANGE FROM BASELINE IN THE WEEKLY AVERAGE OF DAILY WPI SCORES AT WEEK 12 OF THE DOUBLE-BLIND TREATMENT PHASE

This variable, based on an NRS-11, will be analyzed via similar methods to those for the primary efficacy variable.

9.5.2 PROPORTION OF RESPONDERS WITH A $\geq 30\%$ AND $\geq 50\%$ REDUCTION FROM THE OPEN-LABEL TITRATION PHASE BASELINE IN API SCORE OVER TIME

Percent reduction from the Open-Label Titration Phase baseline in NRS score to a given post-baseline week will be derived as $100 * (\text{Titration Baseline pain score} - \text{Post-Baseline WAAPI}) / (\text{Titration Baseline pain score})$. A subject is a responder if the percent reduction is at least 30% and 50%.

This variable will be analyzed using the chi-square test. The percentages, the difference of the percentages, and the two-sided 95% confidence interval of the treatment difference will be presented. The 95% confidence intervals of the treatment difference will be calculated using normal approximation.

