11.3.3. Missing Value Imputation

Unless otherwise stated, all other missing values will not be imputed.

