9.3 PRIMARY ANALYSIS

The primary analysis will be performed based on the mITT Population.

WAAPI over time will be performed by longitudinal data analysis using mixed-model repeated measures (MMRM) methods. All post-randomization baseline observations will be utilized; missing values will remain as missing (i.e. no attempt will be made to impute missing values, and only observed values will be used in the data analysis). The model will include treatment, post-baseline weeks, treatment by week interaction as fixed effects, and baseline WAAPI as the covariate. The covariance will assume to be unstructured. If the estimates do not converge, SAS default covariance structure (variance components) will be assumed. The MMRM with maximum likelihood estimation will utilize the following pseudo-SAS code for analysis:

```
proc mixed data = WAAPI Data method = ml;
class treatment week subject;
model Change in WAAPI = treatment week treatment*week baseline;
repeated week / subject = subject type = un;
lsmeans treatment / pdiff cl e;
lsmeans treatment*week /slice = week cl diff;
ods output diffs = alldiff;
```

If the estimation under type=un cannot converge, the SAS default (variance components) will be used. The estimated treatment effects, treatment differences, and the two-sided 95% confidence intervals of the treatment differences at all post-baseline timepoints will be presented. The primary comparison will be the treatment difference at Week 12.

A clear advantage of using MMRM is that this method does not require artificial missing imputations that would often create biases. The MMRM method is valid if the “missing at random” assumption holds. The trial is designed to minimize missing values: (a) Subjects who discontinue taking study medication are permitted to remain in the study, and safety and efficacy data will continue to be collected from these subjects; (b) Liberal use of rescue medication is allowed during the study, and data collection will continue even after subjects take these medications, and (c) Robust efficacy data collection procedures will be used in the trial.

Using the procedures above, it is expected that missing values will be minimal and that “missing at random” is a reasonable assumption. Therefore, the “MMRM without missing” imputation is reasonable. Sensitivity analyses of missing value imputations will be performed to support the robustness of the conclusion (see [Section 9.4](#)).

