9.4 SENSITIVITY ANALYSES

Missing values sensitivity analyses:

As the MMRM analysis does not impute missing values, sensitivity analyses with various missing value imputation methods will be performed. Sensitivity analyses based on the random replace and tipping point methods will be performed to assess the robustness of the primary efficacy data.

If all daily ratings are missing for a given week, the missing change from baseline values at a given week will be imputed using the following methods.

Random replacement method

Missing change from baseline in WAAPI at Week J will be imputed with randomly generated values from a normal distribution using a seed of 153928221. The normal distribution will be assumed to have a mean x and a standard deviation of y , where x and y are the mean and standard deviation of the changes at Week J based on all subjects (i.e., subjects from both treatment groups) with non-missing values. It should be noted that, if treatment is effective, the results of this missing value imputation method will be more conservative (i.e., biased in favor of the control).

Tipping point method

Missing change values at Week J from placebo subjects will be imputed with the value that is equal to the mean changes among placebo subjects at that week. Missing change values from active treatment subjects will be imputed with the value that is $k\%$ worse than the mean WAAPI from the placebo group at that week, where $k=0, 5, 10, 20, 30, 40 \dots 100$, until tipping (i.e., the treatment difference at Week 12 is no longer significant at a two-sided significance level of 0.05).

Additional Sensitivity Analyses:

Inclusion of paper diary data from the primary analysis

The primary efficacy variable will be analyzed including available paper diary data collected.

Exclusion of weekly average diary entries that do not have at least 5 daily entries during randomization baseline week (Week -1) and at the end of treatment (Week 12)

The primary efficacy variable will be analyzed after treating WAAPI for any giving week as missing if average pain scores are available for less than 5 days in that week.)

Exclusion of subjects who do not complete at least 4 weeks of treatment

The primary efficacy variable will be analyzed in subjects who participate in the study for at least 4 weeks of the double-blind period.

Exclusion of subjects who do not complete at least 8 weeks of treatment

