9.6 EXPLORATORY EFFICACY OUTCOMES

The exploratory efficacy endpoints are as follows:

- Percentage of subjects with a 70% or greater decrease in API from the Open-Label Titration Phase baseline to Week 12 of the Double-Blind Treatment Phase
- Change from baseline to Week 12 of the Double-Blind Treatment Phase in Clinical Global Impression of Improvement (CGI-I) scale (as assessed by the Investigator).

9.6.1 PROPORTION OF RESPONDERS WITH A $\geq 70\%$ REDUCTION FROM THE OPEN-LABEL TITRATION PHASE BASELINE TO WEEK 12 OF THE DOUBLE-BLIND TREATMENT PHASE IN API SCORE OVER TIME

Percent reduction from the Open-Label Titration Phase baseline in NRS score to a given post-baseline Week will be derived as $100 * (\text{Titration baseline pain score} - \text{Post-Baseline API}) / (\text{Titration baseline pain score})$. A subject is a responder if the percent reduction is at least 70%. A subject with missing API for a given post-baseline week will be considered as a non-responder.

This variable will be analyzed using the chi-square test. The percentages, the difference of the percentages, and the two-sided 95% confidence interval of the treatment difference will be presented. The 95% confidence intervals of the treatment difference will be calculated using normal approximation.

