9.8 ADJUSTMENTS FOR MULTIPLICITY

There is only one primary comparison for the study. The clinical efficacy endpoints listed below are listed in order of hierarchical importance:

1. The primary efficacy endpoint, which is change from baseline in WAAPI at last week of treatment;
2. Change from baseline in the weekly average of daily WPI scores at last week of treatment of the Double-Blind Treatment Phase, based on an NRS-11;
3. Percentage of subjects with a 50% or greater decrease in API from the Open-Label Titration Phase baseline to the last week of treatment of the Double-Blind Treatment Phase;
4. Percentage of subjects with a 30% or greater decrease in API from the Open-Label Titration Phase baseline to the last week of treatment of the Double-Blind Treatment Phase;
5. Time to loss of efficacy, defined as discontinuation from the study or study drug for lack of efficacy;
6. Change from baseline to last week of treatment of the Double-Blind Treatment Phase in PGI-I scale (as assessed by the subject);
7. Change from baseline to last week of treatment of the Double-Blind Treatment Phase in WPAI score;
8. Change from baseline to last week of treatment of the Double-Blind Treatment Phase in EuroQoL Group EQ-5D-5L score; and
9. Rescue medication usage during the Double-Blind Treatment Phase.

The null hypotheses of no treatment difference for the above endpoints will be tested at a two-sided significance level of 0.05 in the order specified. To protect the family-wise two-sided p-value at the 0.05 significance level, the treatment superiority for an endpoint cannot be claimed, unless the superiority claims for all prior endpoints in the list, if any, have been established.

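### The 30% and 50% responder endpoints have no missing-data rule and no stated denominator, so the analysis at ranks 3 and 4 of the testing sequence is open

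*SAP*

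**What the plan says.** - SAP 9.5.2 computes percent reduction from the titration-phase baseline score to the WAAPI of a given week. It then states "A subject is a responder if the percent reduction is at least 30% and 50" per cent, and "This variable will be analyzed using the chi-square test". It has no sentence on missing scores and no denominator.
- SAP 9.6.1 uses a parallel formula and the same test for the exploratory 70% endpoint, and adds: "A subject with missing API for a given post-baseline week will be considered as a non-responder". Nothing extends that sentence to 9.5.2.
- Protocol 11.3.3 sets the default: "Unless otherwise stated, all other missing values will not be imputed".
- SAP 9.3 takes the same line for the primary MMRM, where "missing values will remain as missing".
- SAP 9.4 limits its imputation analyses to the primary endpoint: "Sensitivity analyses based on the random replace and tipping point methods will be performed to assess the robustness of the primary efficacy data".
- The timepoint differs between sections. The list in SAP 9.5 reads "Percentage of subjects with a 30% and 50% or greater decrease in API from the Open-Label Titration Phase baseline to Week 12", while the hierarchy in SAP 9.8 reads "Percentage of subjects with a 50% or greater decrease in API from the Open-Label Titration Phase baseline to the last week of treatment".

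**The concern.** The rule is written for the responder endpoint with the least at stake and left out for the two under alpha control. Without a WAAPI the percent reduction cannot be computed. With no imputation by default, a programmer following the text would most naturally leave those subjects out of both numerator and denominator. The remaining group is selected after randomisation. In a randomised-withdrawal trial the reasons for leaving are likely to differ by arm: Protocol 8.1.5 expects that subjects on placebo may have more pain.

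The SAP justifies not imputing in 9.3 by the validity of MMRM under missing at random. A chi-square test on observed cases does not have that protection, because it makes no use of the earlier weekly scores of subjects who leave.

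Under SAP 9.8 no endpoint can be claimed unless every earlier one succeeded. The 50% endpoint is rank 3 and the 30% endpoint is rank 4, so an unstated rule bears on ranks 3 to 9, which is seven of the nine claims.

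**Working it through.** **The plan's own figure.** The documents give no power, response rate or dropout rate for the responder endpoints. The only design figure is for the primary endpoint: 170 per arm, difference 0.7, SD 2, two-sided 5%, power 90% (Protocol 11.4) or over 90% (SAP 9.9). With z = 0.7 / (2 × √(2/170)) = 3.227, power = Φ(3.227 − 1.960) = 0.897. That agrees with 90% to rounding, though it is just under rather than over. The point here takes only the 170 per arm from it.

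**Who would be dropped.** SAP 9.2 averages whatever daily scores exist in a week, and Week 12 is Days 78 to 84, so one entry is enough for a WAAPI. SAP 9 uses electronic diary data only for the pain endpoints. The subjects lost are therefore those with no electronic entry in those seven days.

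**Inputs.** 170 per arm is the planned number; the mITT set will differ because SAP 5.2 removes two sites. All missing and response rates are assumptions, chosen to show a range. SAP 9.3 says only that missing data should be minimal.

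**Formula.** Let x be the responders among the observed subjects, n the number observed, and subscripts A and P active and placebo. The observed-case difference is x_A/n_A − x_P/n_P. With missing as non-response it is x_A/170 − x_P/170. The test is Pearson chi-square without continuity correction: z = difference / √[p(1−p)(1/n_A + 1/n_P)], with p the pooled proportion, and 170 in place of n_A and n_P for the second version.

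| Missing, active / placebo | Observed counts | Observed-case | Missing as non-response |
|---|---|---|---|
| 25% / 40% | 89/127 vs 66/102 | 70.1% − 64.7% = +5.4 points, p=0.39 | 52.4% − 38.8% = +13.5 points, p=0.012 |
| 35% / 20% | 77/110 vs 78/136 | 70.0% − 57.4% = +12.6 points, p=0.041 | 45.3% − 45.9% = −0.6 points, p=0.91 |
| 5% / 10% | 97/162 vs 76/153 | 59.9% − 49.7% = +10.2 points, p=0.069 | 57.1% − 44.7% = +12.4 points, p=0.023 |
| 5% / 5% | 97/162 vs 81/162 | 59.9% − 50.0% = +9.9 points, p=0.074 | 57.1% − 47.6% = +9.4 points, p=0.082 |

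Differences are taken before rounding the percentages.

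**Rounding.** In the second row, 65% of 170 is 110.5, and the observed-case p-value sits on the boundary. With 77 of 111 it is 0.052; with 78 of 111 (70.3% − 57.4% = +12.9 points) it is 0.036. That row shows that the two rules can disagree in size and sign. Its observed-case significance should not be leaned on.

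**Direction.** With more missing on placebo, the observed-case result is less favourable to active than the non-response rule. With more missing on active, it is more favourable.

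**The case against.** A reader might infer that the SAP prescribes a completers-only comparison. The documents do not support that, for three reasons.

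- No denominator is given. The endpoint is worded as a percentage of subjects, and the main efficacy set is mITT, so a programmer could keep everyone in the denominator. The wording in 9.8 could also mean each subject's own last week on treatment, in which case an early leaver still has a score. Protocol 11.3.3 concerns imputation and sets no denominator.
- Completers is the wrong word. SAP 9.3 lets subjects who stop study drug stay in the study with data still collected, and one Week 12 entry suffices. The group lost may be small.
- If missing data are minimal, as SAP 9.3 expects, and similar in both arms, the choice hardly matters. The 5% / 5% row shows this.

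It can also be said that more dropout on active is the less likely pattern, because randomised subjects have already tolerated and responded to a stable dose (Protocol 7.4). In the more likely pattern the observed-case analysis understates the contrast that the non-response rule would show. Nor is the non-response rule neutral: it makes dropout itself part of the outcome. With equal observed response of 50% and 20% / 40% missing (68/136 vs 51/102), the observed-case difference is 0.0, while 68/170 against 51/170 is +10.0 points (p=0.053). A gap between the two rules therefore does not show that either one is false.

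All of this stands and limits the point. It does not remove it. Several defensible analyses of two alpha-controlled endpoints remain open, and the 5% / 10% row shows that modest unequal missingness is enough to move a result across 0.05.

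**Conclusion.** The omission is certain: 9.5.2 has neither a missing-data rule nor a denominator, and 9.6.1 has the rule for the exploratory endpoint only. The consequence is an inference. An observed-case chi-square is the best-supported reading, but the all-mITT and last-week-of-treatment readings cannot be excluded.

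The effect of the choice cannot be computed from the documents. Under the assumed rates it runs from negligible (+9.9 against +9.4 points with 5% missing in each arm) to a change of significance or sign when missingness differs by arm (+5.4 against +13.5, or +12.6 against −0.6). The primary endpoint and the WPI endpoint at rank 2 are unaffected; ranks 3 to 9 are exposed. This should be settled before unblinding.

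**What to change.** In SAP 9.5.2, state that a subject with a missing WAAPI at the analysis week is a non-responder for both the 30% and the 50% endpoint, and that the denominator is all mITT subjects in the arm. Use Week 12 as the timepoint for these endpoints in both 9.5 and 9.8. Without that last step the new sentence would conflict with the hierarchy.

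The cost is a few sentences in a numbered SAP revision made before unblinding. No new data are needed, and the rule is already the sponsor's own in 9.6.1. The downside is that counting missing as non-response is a conservative composite definition, in which leaving the study for any reason is failure. Report the observed-case result, with the number missing by arm, as supportive.

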11.4. Determination of Sample Size

It is estimated that 170 subjects per treatment group will provide 90% power with a 2-sided test at a 5% significance level and standard deviation of API at Week 12 of 2.0 to detect a treatment effect of 0.7 unit (or a standardized effect of 0.35) in change from baseline in the WAAP scores at Week 12 (Double-Blind Phase). Considering a titration success rate of 60%, this study will enroll approximately 875 subjects to obtain 340 subjects achieving a successful dose in order to be randomly assigned to study drug treatment in the Double-Blind Phase.

Additional statistical details will be outlined in the SAP.

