4.4 RANDOMIZATION AND BLINDING

Randomization will be used to avoid bias in the assignment of subjects to treatment, to increase the likelihood that known and unknown subject attributes (e.g., demographics, baseline characteristics) are evenly balanced across treatment groups, and to enhance the validity of statistical comparisons across treatment groups.

During the Open-Label Titration Phase, subjects will be dosed with CAM2038 q1w until a stabilized dose and adequate analgesic effect has been achieved for at least 2 consecutive weeks prior to randomization to the Double-Blind Treatment Phase, in accordance with pre-defined randomization criteria. Subjects whose pain is controlled on 4 mg, 8 mg or 12 mg CAM2038 q1w during the Open-Label Titration Phase will be maintained on 4 mg, 8 mg or 12 mg CAM2038 q1w, or corresponding placebo, during the Double-Blind Treatment Phase. Subjects whose pain is controlled on 16 mg, 24 mg or 32 mg CAM2038 q1w during the Open-Label Titration Phase will be transitioned to CAM2038 64 mg, 96 mg or 128 mg q4w, or corresponding placebo, during the Double-Blind Treatment Phase. Subjects will be randomized to either active CAM2038 or placebo control in a 1:1 ratio within each of the q1w or q4w regimens.

Under normal circumstances, the blind will not be broken until all participants have completed treatment. In case of emergency, and only if the information is required by the Investigator to ensure subject's safety in managing a medical condition, the treatment may be unblinded at the site by using a code-break module. The code-break module will be provided by the Sponsor or designee. If possible, the Investigator should contact the Sponsor prior to unblinding and after any actions have been taken. Whenever a treatment sequence is prematurely unblinded, the reason, date and time of the unblinding, and the individual who broke the blind, must be documented. Individual code breaks will result in withdrawal of the participant from the study.

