9.9 POWER AND SAMPLE SIZE JUSTIFICATION

A sample size of 170 subjects per treatment group will provide over 90% power to detect a treatment difference at a two-sided 5% significance level. In the sample size calculation, a treatment difference of 0.7 units and an SD of 2 (or a standardized effect of 0.35) for the primary efficacy variable were assumed.

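### The responder tests at steps 3 and 4 of the fixed sequence adjust for neither baseline pain score; adjusting for both is cheap and gains about 2–7 points of power per step

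*SAP*

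**What the plan says.** **Responder tests.** SAP 9.5.2 computes 100 × (T − W)/T, where T is the single pain score taken before titration (SAP 6.1) and W is the WAAPI of a post-baseline week. It cuts this at 30% and 50%, and then "This variable will be analyzed using the chi-square test". The difference in percentages gets a normal-approximation interval. No covariate enters. SAP 9.6.1 repeats the scheme at 70% and counts a missing score as non-response; 9.5.2 has no missing-data rule.

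**Primary model.** SAP 9.3: "The model will include treatment, post-baseline weeks, treatment by week interaction as fixed effects, and baseline WAAPI as the covariate". Sections 9.5.1 and 9.5.4–9.5.7 send WPI, PGI-I, WPAI, EQ-5D-5L and rescue days to similar methods.

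**Sequence.** Under SAP 9.8 nine null hypotheses "will be tested at a two-sided significance level of 0.05 in the order specified", and "the treatment superiority for an endpoint cannot be claimed, unless the superiority claims for all prior endpoints in the list, if any, have been established". The 50% responder rate is third and the 30% rate fourth. Behind them stand time to loss of efficacy, PGI-I, WPAI, EQ-5D-5L and rescue use.

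**Power.** Only the primary endpoint has a power statement: "A sample size of 170 subjects per treatment group will provide over 90% power" (SAP 9.9). Protocol 11.4 uses a "standard deviation of API at Week 12 of 2.0 to detect a treatment effect of 0.7 unit". Neither document gives response rates or power for steps 3 and 4.

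**Protocol.** Protocol 9.6.2 lists only a 30% responder endpoint, and 11.3.5 names no test for it. The 50% cut and the chi-square test come from the SAP.

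**The concern.** The start-of-titration score sets the pain level a subject must stay under to count as a responder. The Week 0 WAAPI sets how far from that level the subject stands at randomisation. Both are recorded before treatment is assigned, so using them brings in nothing affected by treatment. A test that leaves out strong predictors of its outcome gives up power.

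Elsewhere that would be a minor inefficiency. Here the two tests act as gates. If either fails, no superiority claim can be made for steps 5–9, even when the drug works exactly as assumed and the primary comparison succeeds.

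**Working it through.** **Inputs from the documents.** 170 per arm, difference 0.7, SD 2, two-sided 5% (SAP 9.8 and 9.9); allocation "in a 1:1 ratio within each of the q1w or q4w regimens" (SAP 4.4); pain score at least 5 before the test dose (Protocol 7.3); 7-day score at most 4 and at least 2 points below the start of titration at randomisation (Protocol 7.4).

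**1. The plan's own figure.** Power = Φ(0.35 × √(170/2) − 1.96) = Φ(3.227 − 1.960) = Φ(1.267) = 0.897. The stated 90% is reproduced to rounding.

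**2. Do the two scores predict response?** For a 50% response W must be at most T/2: 2.5 when T = 5, and 4.5 when T = 9. A subject with T = 5 can be randomised with a Week 0 score of at most 3, a reduction of 2/5 = 40%, so is not yet a 50% responder. A subject with T = 9 and Week 0 = 4 is already at 5/9 = 56%, with 0.5 point to spare; with Week 0 = 2 the margin is 2.5 points. Both scores matter.

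**3. Cost of the cut alone, with no assumed baselines.** Cut a normal outcome with standardised effect 0.35 at the median:
- difference in proportions = Φ(0.175) − Φ(−0.175) = 0.139
- SE = √(0.5/170) = 0.0542
- power = Φ(0.139/0.0542 − 1.96) = 0.726

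Away from the median it falls: 65.5% at a placebo response rate of 0.20, and 55.7% at 0.80.

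**4. Gain from adjustment.** This needs assumptions that the documents do not give. All runs have complete data and a Week 12 difference of 0.7.
- *Set A:* T from 5 to 10; Week 0 SD about 0.72; placebo mean rise 0.7, 1.2 or 1.7; slope of Week 12 on Week 0 of 0.5 or 1.0; Week 12 SD 2.0; six scenarios of 2,500 trials.
- *Set B:* T from 5 to 10 with probabilities 0.15, 0.20, 0.25, 0.20, 0.12, 0.08; Week 0 mean 2.8 with placebo rise 1.0, or mean 3.3 with rise 1.5; residual SD 2 around the Week 0 score; 3,000 trials each (1,500 for the logistic model).

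| Power | Set A | Set B |
|---|---|---|
| 50% cut, chi-square | 66.7–70.2% | 60.6%, 61.9% |
| 50% cut, logistic, both scores | 71.0–76.6% | 66.3%, 66.7% |
| 30% cut, chi-square | 54.6–64.1% | 51.7%, 60.1% |
| 30% cut, logistic, both scores | 57.6–70.2% | 57.6%, 65.6% |
| Uncut percent reduction, both scores | 88.2–92.0% | 86.9%, 87.5% |

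A third run of the same kind gave 66–71% and 60–67% by chi-square, and 73–78% and 63–73% adjusted. The gain within a scenario is about 2–7 points. A wider grid of assumptions gave chi-square power of 57–70% at the 50% cut and 48–70% at the 30% cut, lowest when most placebo subjects still respond.

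*Share of the gap recovered (Set B, 50% cut).* The gap to the uncut analysis is 86.9 − 60.6 = 26.3 points, and adjustment recovers 66.3 − 60.6 = 5.7 of them, about a fifth.

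**5. Effect on the sequence.** Steps 1, 3 and 4 all succeed in 46.0–53.4% of Set A trials with chi-square and 48.8–59.6% with adjustment; the third run gave 50–54% and 54–60%. In Set B the chi-square figures are 41.1% and 46.2%. Given a significant primary result (89.1% and 88.8% of Set B trials), the share stopped at step 3 or 4 is 1 − 0.411/0.891 = 54% and 1 − 0.462/0.888 = 48%. Step 2 was not simulated, so the chance of reaching step 5 is no higher than these joint figures.

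**6. Dropout.** Take assumed response rates of 47% and 59.5%. If missing counts as non-response and 20% drop out of each arm, the rates become 0.376 and 0.476 and power is 46%. With 30% placebo and 20% active dropout they become 0.329 and 0.476, and power is 79%. Across four assumed pairs of rates:
- non-response rule, equal 20% dropout: 32–50%
- non-response rule, placebo dropout 30–35% against 20%: 74–93%
- complete cases only: 44–54%

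**The case against.** **The chi-square test is valid.** This stands. Under 1:1 randomisation it is unbiased, and the fixed sequence controls type I error. The point concerns efficiency only, and the primary endpoint and step 2 are untouched.

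**The 55–70% figure is not a property of the plan.** This also stands. It assumes complete data and invented baseline distributions. This is a withdrawal trial in which Protocol 8.1.5 expects placebo subjects to have rising pain and perhaps leave. If missing means non-response and placebo dropout is clearly higher, responder power could exceed 74%. But 9.5.2 does not state that rule, so the favourable case cannot be counted on.

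**Adjustment does not close the gap.** Correct. A reader might infer that the unadjusted test explains the distance from about 60% to about 90%. It does not: dichotomising accounts for most of it. Setting an unadjusted chi-square against an adjusted full-scale analysis also exaggerates the contrast, since unadjusted percent reduction has about 78–88% power.

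**The order belongs to the sponsor.** A reader might infer that an uncut percent-reduction test should take step 3. The documents do not support requiring that. The 30% and 50% responder rates are named secondary objectives in SAP 4.1, and they ask a different clinical question from a mean. The substitute would nearly repeat step 1: in simulation its test statistic correlated 0.98 with the primary's, and it passed in 97–99% of trials where the primary passed.

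**Conclusion.** The concern holds as a cheap improvement. The responder tests adjust for neither score known before randomisation, and adjusting for both gains about 2–7 points of power per step. Joint success of steps 1, 3 and 4 rises from about 46–54% to about 49–60%, and from a lower start under the Set B assumptions. These sizes rest on 170 per arm, difference 0.7, SD 2, complete data and the assumed baselines. Excluding Sites 068 and 077 from the mITT Population may leave fewer than 170 per arm; the documents do not give the counts.

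Two further inferences are not supported. The responder tests cannot be called the weakest in the plan, because the documents give no basis for computing power at steps 5–9, including the log-rank test at step 5. Nor do they disregard the start-of-titration score altogether: it is the denominator of the outcome. What is missing is adjustment for it.

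**What to change.** In SAP 9.5.2, and for consistency in 9.6.1, replace the chi-square test with a logistic regression of Week 12 responder status on treatment, start-of-titration pain score and Week 0 WAAPI. Use the test of the treatment coefficient for steps 3 and 4. Report the covariate-standardised difference in percentages with its 95% CI, naming the interval method in advance, and keep the raw percentages as the descriptive display. Name a fallback, such as the planned chi-square, in case the model does not converge. The endpoints and their order stay as they are. Either test needs a stated rule for subjects without a Week 12 score; that is a separate gap.

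Optional and supportive only: analyse percent reduction uncut, with a cumulative responder curve by arm. The 9.3 model would need the start-of-titration score added, since its only baseline covariate is WAAPI. Reordering the sequence is not part of this fix.

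Cost: a numbered SAP revision under SAP 6.2 before unblinding and a few lines of code, with no new data or subjects. The downside is a model-based test in place of a simple table, with standardisation needed to stay on the percentage-point scale.
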